### **Publications:**

All protocol- and amendment-related information, with the exception of the information provided by Imago on public registry websites, is considered confidential information. Study results may also be presented at one or more medical congresses and may be used for scientific exchange and teaching purposes. Additionally, this study and its results may be submitted for inclusion in all appropriate health authority study registries, as well as publication on health authority study registry websites, as required by local health authority regulations. Eligibility for external authorship, as well as selection of first authorship, will be determined by the study Principal Investigator(s).

## 11 Data and Safety Monitoring Oversight

A Data and Safety Monitoring Plan is required for all individual protocols conducted at Mays Cancer Center. All protocols conducted at Mays Cancer Center are covered under the auspices of the Mays Cancer Center Institutional Data Safety Monitoring Plan (DSMP).

The Mays Cancer Center Institutional DSMP global policies provide individual trials with:

- institutional policies and procedures for institutional data safety and monitoring,
- an institutional guide to follow,
- monitoring of protocol accrual by the Mays Cancer Center Protocol Review Committee,
- review of study forms and orders by the Forms Committee,
- tools for monitoring safety events,
- independent monitoring and source data verification by the Mays Cancer Center QA Monitor/Auditor
- monitoring of UPIRSO's by the Director of Quality Assurance and DSMC,
- determining level of risk (Priority of Audit Level Score – PALS),
- oversight by the Data Safety Monitoring Committee (DSMC), and
- verification of protocol adherence via annual audit for all Investigator Initiated Studies by the Mays Cancer Center Quality Assurance Division.

### **Monitoring Progress and Safety**

Due to the risks associated with participation in this protocol, the Mays Cancer Center DSMB in conjunction with the Principal Investigator will perform assessment of adverse events, adverse event trends and treatment effects on this study. The Mays Cancer Center DSMB acts as an independent Data Safety Monitoring Board (DSMB) for IIS conducted at Mays Cancer Center. The Mays Cancer Center DSMB will monitor data throughout the duration of a study to determine if continuation of the study is appropriate scientifically and ethically. An additional layer of review is provided by the Mays Cancer Center Data Safety Monitoring Committee (DSMC) who will review DSMB quarterly reports.

Baseline events and adverse events will be captured using the Mays Cancer Center Master Adverse Events Document for each patient using CTCAE V.5.0 or most current version for the grading and attribution of adverse events. Usage of the Mays Cancer Center Master Adverse Events Document centrally documents:

- the event and evaluates the seriousness, and grades the severity of the event,
- if the event was a change from baseline,
- the determination of the relationship between the event and study intervention,
- if the event was part of the normal disease process, and
- what actions were taken as a result of the event.

Safety Definitions:

For this study, the following safety definitions will be applicable:

**Adverse Event Definition:** An adverse event (AE) is defined as any untoward or unfavorable medical occurrence in a human subject, including any abnormal sign (for example, abnormal physical exam or laboratory finding), symptom, or disease, temporally associated with the subject's participation in the research, whether or not considered related to the subject's participation in the research. For this study, all adverse events will be documented starting with day 1 of treatment and ending 28 days after the last dose of study drug is received. Events occurring pre-first dose are baseline events and not AEs.

**Serious Adverse Event Definition:** is any adverse event that:

1. results in death;
2. is life-threatening (places the subject at immediate risk of death from the event as it occurred);
3. results in inpatient hospitalization or prolongation of existing hospitalization;
4. results in a persistent or significant disability/incapacity;
5. results in a congenital anomaly/birth defect; or
6. based upon appropriate medical judgment, may jeopardize the subject's health and may require medical or surgical intervention to prevent one of the other outcomes listed in this definition

Adverse event intensity will be evaluated using the National Cancer Institute (NCI) Common Terminology Criteria for Adverse Events (CTCAE) version 5.0, published 27 November 2017. For adverse events (AEs) not included in the CTCAE, the following guidelines will be used to describe severity.

**Mild** – Events require minimal or no treatment and do not interfere with the participant's daily activities.

**Moderate** – Events result in a low level of inconvenience or concern with the therapeutic measures.

Moderate events may cause some interference with functioning.

**Severe** – Events interrupt a participant's usual daily activity and may require systemic drug therapy or other treatment. Severe events are usually potentially life-threatening or incapacitating. Of note, the term "severe" does not necessarily equate to "serious".

All adverse events (AEs) must have their relationship to study intervention assessed by the clinician who examines and evaluates the participant based on temporal relationship and his/her clinical judgment. The degree of certainty about causality will be graded using the categories below.

- **Unrelated:** There was no relationship of the adverse event to the use of the drug or biologic. This may include, but is not limited, to the adverse experience being an expected outcome of a previously existing or concurrent disease, concomitant medication or procedure the subject experienced during their treatment period.
- **Remote/Unlikely:** Adverse events which are judged probably not related to the drug or biologic.
- **Possible:** There was no clear relationship of the adverse event to the use of the drug or biologic; however, one cannot definitively conclude that there was no relationship.

- Probable: While a clear relationship to the drug or biologic cannot be established, the event is associated with an expected adverse event (per the current Investigator Brochure or DSMC findings) or there is no other medical condition or intervention which would explain the occurrence of such an experience.
- Definite: The relationship of the use of the drug or biologic to the experience is considered definitively established.

If a causal relationship is considered probable, possible, or definite by the Investigator, the AE is considered to be “related” for purposes of regulatory reporting. If a causal relationship is considered remote/unlikely or unrelated, the AE is considered “unrelated” for purposes of regulatory reporting.

**Unanticipated Problems Involving Risks to Subjects or Others Definition:** Unanticipated problem involving risk to subjects or others includes any incident, experience or outcome that meets all of the following criteria:

- A. unexpected (in terms of nature, severity, or frequency) given (a) the research procedures that are described in the protocol-related documents, such as the IRB-approved research protocol and informed consent document; and (b) the characteristics of the subject population being studied (note: the unfounded classification of a serious adverse event as “anticipated” constitutes serious non-compliance);
- B. definitely related or probably related to participation in the research; and
- C. suggests that the research places subjects or others at a greater risk of harm (including physical, psychological, economic, or social harm) than was previously known or recognized.

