### **5.4 Inclusion and Exclusion Criteria**

#### **5.4.1 Inclusion Criteria**

Inclusion criteria are as follows:

1. Age  $\geq 18$  years.
2. Diagnosis of Essential Thrombocythemia per World Health Organization (WHO) diagnostic criteria for myeloproliferative neoplasms ([Arber et al., 2016](#)).
3. Patients who are intolerant or resistant to hydroxyurea per ELN criteria, or in the Investigator's judgment are not candidates for available approved therapy. The ELN definitions of resistance/intolerance to HU requires the fulfillment of at least one of the following criteria:
  - Platelet count  $>600 \times 10^9$ /L after a daily dose of at least 2 g HU for at least 3 months (2.5 g/day in patients with a body weight over 80 kg);
  - Platelet count  $>400 \times 10^9$ /L and WBC  $<2.5 \times 10^9$ /L at any dose of HU;
  - Platelet count  $>400 \times 10^9$ /L and hemoglobin  $<10$ g/dL at any dose of HU
  - Presence of unacceptable HU-related non-hematologic toxicities, including fever, mucocutaneous manifestations or leg ulcers.
4. Requires treatment in order to lower platelet counts based on the Clinically Relevant IPSET-Thrombosis Guidelines.
5. Platelet count  $>450 \times 10^9$ /L pre-dose Day 1.
6. Peripheral blast count  $\leq 5\%$  pre-dose Day 1.
7. ANC  $\geq 0.5 \times 10^9$ /L pre-dose Day 1.
8. Fibrosis Score  $<$ grade 2, as per a slightly modified version ([Arber et al., 2016](#)) of the European Consensus Criteria for Grading Myelofibrosis, ([Thiele et al., 2005](#)).

9. Life expectancy > 36 weeks.
10. Able to swallow capsules.
11. Amenable to spleen size determination, bone marrow evaluations (in the ITP only, optional in the ATPs), and peripheral blood sampling during the study.
12. Must have discontinued ET therapy at least 2 weeks (4 weeks for interferon) prior to study drug initiation.
13. Agrees to use an approved method of contraception from Screening until 28 days after last administration of the study drug. Acceptable methods of birth control include: birth control pills, depo-progesterone injections, a vaginal hormonal contraceptive ring, a barrier contraceptive such as a condom with spermicide cream or gel, diaphragms or cervical cap with spermicide cream or gel, or an intrauterine device (IUD).
14. If male, agrees not to donate sperm or father a child for at least one month after the last dose of the study medication.

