### 7.2 Screening (Day -28 to Day -1)

- Review of all Inclusion and Exclusion Criteria
- Complete medical/medication history including:
  - History of their current disease (see Section 12.2)
  - Calculate ECOG performance status (Section 12.5)
  - History of all treatments for their current disease [including clinical course with hydroxyurea (see Section 12.3) and/or other ET therapy] or any previous oncologic conditions; including chemical, surgical and/or radiotherapeutic
  - All concomitant medication, in addition to any used in the 15 days prior to Screening
  - Transfusion history, including: the average number of transfusions per month and average volume of each transfusion over a 6-month period; and, any transfusions received (RBC, platelets, etc.), with approximate volumes, within 30 days prior to Screening
- Full PE, including Vital Signs – review of all body systems as indicated by signs/symptoms
- Spleen length in centimeters for subjects with palpable splenomegaly
- Collect blood for the following Local Laboratory assessments:
  - CBC with manual differential
  - Chem-12
  - Coagulation (PT/INR/aPTT)
  - C-reactive protein
  - Testing of mutant (variant) allele burden in granulocytes
  - Serum pregnancy test for WOCBP
- Bone Marrow Sampling, including additional aspirate for storage
- Collect MPN-SAF as close to Day -7 as possible and provide patient with questionnaire for completion on Day 1, prior to or at the start of the visit (i.e., pre-dose)

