## 7.7 Schedule of Events – Initial Treatment Period

INITIAL TREATMENT PERIOD		Weekly Visits ( $\pm 1$ day)										Bi-Weekly Visits ( $\pm 2$ days) a				Monthly Visits ( $\pm 3$ days) a		Follow-up ( $\pm 3$ days)	
Procedures	Screen	Day 1	Day 8 Week 1	Day 15 Week 2	Day 22 Week 3	Day 29 Week 4	Day 36 Week 5	Day 43 Week 6	Day 50 Week 7	Day 57 Week 8	Day 71 Week 10	Day 85 k Week 12	Day 99 Week 14	Day 113 k Week 16	Day 141 k Week 20	Day 169 or EOT Week 24	Pre-EOS	EOS/ET	
Informed Consent	1																		
Inclusion/Exclusion	1																		
Demographics	1																		
Physical Exam g	1	1	1	1	1	1	1	1	1	1	1k	1	1k	1k	1	1	1		
MPN-SAF h	1	1	1	1	1	1	1	1	1	1	1	1	1	1	1	1	1		
Adverse Events	1	1	1	1	1	1	1	1	1	1	1	1	1	1	1	1	1		
Concomitant Medications	1	1	1	1	1	1	1	1	1	1	1	1	1	1	1	1	1		
ECOG	1										1					1			
Bone Marrow Biopsy and Aspirate (and pathology) i	1															1c	1d		
Titration Assessment			1j	1j	1j	1j	1j	1j	1j	1j	1j	1j	1j	1j	1j				
Qualification Assessment																	1d		
Dispense IMG-7289	1	1f	1f	1f	1f	1	1	1	1	1	1	1	1	1	1				
Administer IMG-7289		←													→				
Clinical Laboratory																			
CBC with manual Diff	1	1	1	1	1	1	1	1	1	1	1	1	1	1	1	1	1		
Chem-12 (CMP)	1	1				1				1		1		1	1	1	1		
C-reactive protein	1	1				1				1		1		1	1	1	1		
Testing of mutant allele burden in granulocytes	1															1			
PT/INR/aPTT	1																		
Pregnancy Test- Serum b	1	1																	

Data collection may begin after subject has consented to participation; % NCI-CTCAE v5.0 will be used to document adverse events. Adverse events should only be collected starting on Day 1 of treatment.

- a: It is anticipated that by Week 8 all patients will have achieved a stable dose, with weekly visits no longer required. For safety purposes, weekly (or bi-weekly, as appropriate) visits may continue to be implemented at PI's discretion, if necessary. CBC with manual diff only is required at weekly visits; at bi-weekly visits, titration assessment is also required.
- b: Serum pregnancy test for women of childbearing potential (women who are not post-menopausal for 1 year or more) also performed if pregnancy suspected while patient remains on-study.
- c: Optional not required .

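### Serious pre-dose events from the required screening marrow or a study-driven stop of ET therapy have no mandatory SAE route, because everything before the first dose is classed as not an AE

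*Combined protocol and SAP*

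**What the plan says.** Section 11 (Monitoring Progress and Safety) defines an AE broadly, as an untoward occurrence "temporally associated with the subject's participation in the research, whether or not considered related to the subject's participation in the research". The same paragraph then narrows this: "For this study, all adverse events will be documented starting with day 1 of treatment and ending 28 days after the last dose", followed by "Events occurring pre-first dose are baseline events and not AEs". A serious adverse event "is any adverse event that" meets one of six seriousness criteria.

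The Day 1 start is repeated elsewhere. The note under the Section 7.7 schedule reads "Adverse events should only be collected starting on Day 1 of treatment", Section 7.8 carries the same note, and the synopsis places AE assessment after the first dose.

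Two study requirements fall before that point:

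- Section 7.2 lists, at screening, "Bone Marrow Sampling, including additional aspirate for storage".
- Inclusion criterion 12 (Section 5.4.1) states: "Must have discontinued ET therapy at least 2 weeks (4 weeks for interferon) prior to study drug initiation".

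**The concern.** The general definition follows participation in the research, and participation starts at consent: Section 7.1 puts consent ahead of every study-related procedure. The exclusion follows the first dose instead. Between the two, patients undergo a marrow aspirate and biopsy with extra material taken for storage, and some may stop cytoreductive treatment in order to qualify. These patients need platelet lowering (inclusion criterion 4) and must still be above 450 x 10^9/L on Day 1 (criterion 5). Section 3.1 lists raised rates of thrombosis and bleeding among the features of ET.

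At stake is oversight of harm that comes from a study requirement rather than from the drug. Patients harmed before dosing, who may then never be dosed, are the easiest to lose from safety reporting.

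**Working it through.** The plan states no figure to reproduce. The check sets the definitions, the collection window and the reporting table side by side.

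**Step 1: is a pre-dose event an AE?** By the general definition ("temporally associated with the subject's participation in the research"), a complication of the post-consent screening marrow is one. By the closing sentence of the same paragraph, it is not. The wording introduced for this study is the specific rule, and the synopsis and the schedule notes agree with it. In practice, therefore, the answer is no.

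**Step 2: can it be an SAE?** SAEs are a subset of AEs, so no. No section makes an exception for protocol-required procedures or for washout.

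**Step 3: which reporting lines are lost?** From the SAE/UPIRSO table in Section 11:

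| Line in the table | Applies to a serious pre-dose event? |
|---|---|
| All SAEs and UPIRSOs to Regulatory Affairs, Imago and the Director of Quality Assurance, as soon as possible | Not as an SAE |
| SAE to the PI within 24 hours | No |
| SAE to the IRB annually | No |
| Unexpected SAE related to study treatment, to FDA | No; without a dose it could not be related to treatment in any case |
| UPIRSO lines | Only if the UPIRSO definition is met |

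**Step 4: does the UPIRSO route replace them?** That definition is not limited to AEs. It does require all three of the following: the event is unexpected given the procedures and the population; it is probably or definitely related to participation; and it suggests greater risk than was known. A recognised marrow complication, or a thrombosis in ET, could fail the first or third criterion. An event only possibly related fails the second.

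**Step 5: how much of the study lies outside the window?**

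- Inputs: screening up to 28 days, treatment 24 weeks = 168 days, follow-up 28 days.
- 28 + 168 + 28 = 224 days = 32 weeks, which agrees with the duration in the synopsis.
- 28 / 224 = 12.5%, as an upper limit on the share of calendar time.
- Marrows: the synopsis requires 2 per patient in the initial period, one of them at screening. For 20 treated patients, 20 x 1 = 20 of 20 x 2 = 40 precede Day 1. Marrows in screen failures are additional.
- Washout: the minimum (14 days, or 28 for interferon) runs up to the first dose, so all of it falls outside the window.

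**The case against.** The Day 1 start is stated consistently in several places, so it is a deliberate choice and not a slip. Much of a pre-dose event would also remain visible. Baseline events go into the same Master Adverse Events Document as AEs, which records seriousness and severity. The PI reviews those documents continuously and reports to the DSMB quarterly, on a form that includes morbidity and mortality. UPIRSO covers any incident, and an event may be unexpected in severity or frequency as well as in kind. The consent form, against which expectedness is partly judged, is not among the documents available here.

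Nor is everything before Day 1 imposed by the study. Criterion 12 is an eligibility condition, and some patients may be off therapy before consent. The screening marrow also informs eligibility (fibrosis grade and the WHO diagnosis); only the stored aspirate is clearly for research alone.

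These points stand, and they rule out stronger readings. A reader might infer that the trial would report no harm from its washout or marrow whatever happened, or that the DSMB and IRB would not be told. The documents do not support either inference, because the baseline log, the PI's review and the UPIRSO route all exist. A reader might also infer that a pre-dose injury would mask later AEs by becoming part of the baseline. But the Master document records whether an event is a change from baseline, so later worsening can still be captured.

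The objection does not supply a mandatory route. Each of these channels depends on the PI's judgement or on the three UPIRSO criteria, and none requires a serious pre-dose event to be reported as an SAE. A deliberate Day 1 start for drug-related AEs also does not explain why procedure-related events after consent should be excluded.

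**Conclusion.** The point holds as a gap in mandatory reporting, not as a loss of all visibility. Under the definitions as written, a serious complication of the required screening marrow, or a serious event after a study-driven stop of ET therapy, is neither an AE nor an SAE. The as-soon-as-possible notice, the 24-hour notice to the PI and the annual IRB report therefore do not apply to it as an SAE.

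The marrow part concerns every patient screened to completion. The washout part concerns only patients who stop therapy after consent in order to enter, and the documents do not say how many that will be. They also give no rate for washout thrombosis or marrow complications, so no expected number of affected events is offered. The 12.5% is a share of time, not of risk.

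The conclusion assumes that the institutional monitoring plan and guidelines cited in Section 11, which were not available, do not already require such reports. The primary endpoint, the Simon design and its decision rules are untouched. This is a cheap improvement to safety oversight.

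**What to change.** Reconcile the AE definition in Section 11 with its closing sentence, and align the notes under 7.7 and 7.8 and the synopsis line on AE assessment. The revised rule would read in substance as follows:

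- From consent to first dose, record as AEs or SAEs all serious events, and any event attributed to a protocol-required procedure or to study-driven discontinuation of ET therapy.
- Route them through the Section 11 reporting table, including for patients who are never dosed.
- Tabulate them separately from treatment-emergent AEs, which still start on Day 1.
- Leave all other pre-dose conditions as baseline events.

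The washout length and all clinical rules stay as they are.

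The cost is a short text change and a few extra SAE reports. No new visit is needed, since the Master Adverse Events Document already captures baseline events. The log in Appendix 12.8 already separates study attribution from drug attribution and has a code for subjects who did not receive the intervention.

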#### Reporting Requirements

For this study, the Master Adverse Events Documents collected on patients for this protocol will be reviewed by the Principal Investigator on a continuous basis to determine if a serious safety problem has emerged that result in a change or early termination of a protocol such as:

- suspending enrollment due to safety or efficacy, or
- termination of the study due to a significant change in risks or benefits.

The PI will provide the DSMB with the quarterly findings for discussion and review during their meetings.

The PI (or designee) is responsible for notifying sub-investigators regarding recommendations to modify the dosage (dose escalate, dose decrease – outside of the per patient defined titration plan) to ensure that subsequent subjects are treated at the currently approved dose level. As per the protocol, the PI will contact Imago medical staff to discuss protocol modifications for the management of clinically significant changes in platelets, neutrophil counts, or other hematologic parameters. Discussions with Imago staff will be documented and decisions shared with the DSMB and all sub-investigators. In the event starting doses are modified, the PI may delegate the study coordinator to notify other Mays staff, including the Investigational Drug Section to ensure that orders are modified timely and appropriately.

Additionally, this study will have an interim analysis after the first 9 patients to review for response rate. The results of the first 9 patients should be shared with the DSMB to approve extending the study to an additional 11 subjects. The PI is responsible to for notifying sub-investigators of the hold on enrollment until the DSMB has recommended continuance of the study.

Stopping rules for this study include 2 DLT's in the first cohort of 9. A DLT is defined as any one of the following AEs that occurs through Day 7 of the Initial Treatment Period unless the event is considered by the Investigator to be clearly unrelated to IMG-7289:

- Any Grade 3 or above thrombocytopenia associated with clinically significant bleeding\*;
- Any Grade 4 thrombocytopenia associated with the requirement for platelet transfusion;
- Any Grade 4 or 5 non-hematologic adverse event;
- Any Grade 3 or above non-hematologic adverse event with the following exceptions:
  - Nausea, vomiting or diarrhea lasting 3 days or less

- Aesthesia lasting less than 7 days
- Any Grade 3 electrolyte abnormality unrelated to the underlying malignancy and persisting greater than 24 hours.

\*A clinically significant bleeding event is defined as an event that is life-threatening, cannot be controlled and/or results in hemodynamic instability.

As per the Mays Cancer Center DSMP, any protocol modifications, problematic safety reports, unanticipated problems, and suspension or early termination of a trial must be reported to the DSMB and all members of the research team. Furthermore, the PI of this study will promptly notify all study affiliates, the UT Health SA IRB, the Mays Cancer Center DSMB, and the FDA via a FDA Form 3500Aa written IND safety report of any serious adverse events that are unexpected and also suspected by the Investigator to be related to the use of the study treatment (deemed possibly, probably or definitely related). Suspension and early termination of a trial must also be reported immediately to the Director of Quality Assurance who will promptly notify the sponsor and the UT Health SA IRB.

The PI will review the Master Adverse Events documents to determine the significance of the reported events and will provide findings using the Investigator Initiated Study Quarterly DSMB Report Form on a quarterly basis with the DSMB. The DSMB will review the information provided by the PI and report to the Mays Cancer Center DSMC on a quarterly basis, unless an emergent issue has been identified. The Investigator Initiated Study Quarterly DSMB Report Form includes information on adverse events, current dose levels, number of patients enrolled, significant toxicities per the protocol, patient status (morbidity and mortality) dose adjustments with observed response, and any interim findings. Any trend consisting of three or more of the same event will be reported to the Mays Cancer Center DSMB for independent review outside of the quarterly reporting cycle, which begins the quarter after the first patient is enrolled on the protocol. The DSMB will also provide its findings to the Mays Cancer Center's Regulatory Affairs Division so that it may be provided to the UT Health SA IRB with the protocol's annual progress report. Conflict of interest is avoided by the independent reviews of the Mays Cancer Center DSMB, Mays Cancer Center DSMC, and by ongoing independent review of UPIRSO trends by the Director of Quality Assurance.

All SAE and UPIRSO's will be reported following Mays Cancer Center, UT Health SA institutional and FDA guidelines.

UT HEALTH SA SAE/UPIRSO REPORTING REQUIREMENTS For IIS that the PI holds the IND		
Type Event	Report to	Timeframe
All, SAE and UPIRSO	Regulatory Affairs, Imago BioSciences and DQA	ASAP
All SAEs deemed both unexpected and 'related*' to study treatment and UPIRSO	FDA on form 3500A	within 7 calendar days by telephone and 15 calendar days using the Form 3500A
SAE	PI at UT Health SA	within 24 hours
SAE	UT Health SA IRB	Annually
UPIRSO – all	PI at UT Health SA	within 24 hours
UPIRSO – all	FDA	within 7 days
UPIRSO - life threatening	UT Health SA IRB/UT Health SA OCR	within 48 hours
UPIRSO - non-life threatening	UT Health SA IRB/UT Health SA OCR	within 7 days

\*deemed possibly, probably or definitely related

SAEs that are unexpected and also suspected by the Investigator to be related to the use of the study treatment (deemed possibly, probably or definitely related) that occur during clinical trials with or without an Investigational New Drug (IND) application are mandatory reports submitted to FDA via Medwatch FDA F3500A *within 15 days for events that have at least a possible relationship with the drug.*

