Observations regarding dose-response in patients with MF treated in the CTP-102 study have led to modifications of the titration schedule. As additional patients have been treated, it has been noted that for a given daily dose, the platelet count continues to fall beyond Day 7 of dosing, i.e., two successive weekly up-titrations caused the platelet count to fall more than expected and occasionally led to significant thrombocytopenia. In those patients who had received an identical dose for 3 consecutive weeks, each experienced a drop (mean -31%; N=20) in the platelet count between Day 7 and Day 14. The mean decrease in platelet counts from Day 14 and Day 21, however, was approximately -12%, suggesting that a steady state of drug exposure, LSD1 activity and platelet production occurs between Day 21 and Day 28. As such, it appears that two or three weeks between up-titrations is an insufficient amount of time for both the plasma concentrations of the drug and platelet production to reach a new steady-state necessary to achieve a stable platelet count. Therefore, up-titrations may occur no more frequently than every four weeks from the previous up- or down-titration. Down-titrations can occur at any time in best interest of the patient.

At the doses proposed in this study, the concentration of IMG-7289 is sufficient to inhibit hematopoiesis for a fraction of the 24-hour dosing period, thus allowing LSD1 activity to return and resume its function in normal thrombopoiesis. Chronic daily administration of IMG-7289 in rat, dog and humans has been well tolerated. No safety signals have been observed in either the AML/MDS or myelofibrosis studies with IMG-7289 at doses up to 6 mg/kg/d. Please refer to the Investigator's Brochure for additional information on the non-clinical and clinical studies conducted to date with IMG-7289.

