### 6.5.2 Dose Limiting Toxicities

DLT is defined as any one of the following AEs per CTCAE version 5.0 criteria that occurs through Day 7 of the Initial Treatment Period will be considered DLTs unless the Investigator deems the AE to be clearly unrelated to IMG-7289:

- Any Grade 3 or above thrombocytopenia associated with clinically significant bleeding\*;
- Any Grade 4 thrombocytopenia associated with a requirement for platelet transfusion;
- Any Grade 4 or 5 non-hematologic adverse event;
- Any Grade 3 or above non-hematologic adverse event with the following exceptions:
  - Nausea, vomiting or diarrhea lasting 3 days or less
  - Aesthenia lasting less than 7 days
- Any Grade 3 electrolyte abnormality unrelated to the underlying malignancy and persisting greater than 24 hours.

*\*A clinically significant bleeding event is defined as an event that is life-threatening, cannot be controlled and/or results in hemodynamic instability.*

Patients who experience DLT will have their dose adjusted downward by 50% if the Principal Investigator deems it safe for the patient to continue on IMG-7289; the titration rules will subsequently be followed. Any patient that experiences DLT that results in discontinuation of IMG-7289 therapy may begin alternative therapy within 24-48 hours of discontinuation if their physician deems this safe and appropriate regarding the resolution of the DLT.

Please consult the Principal Investigator for IMG-7289 dose modifications for the management of clinically significant changes in platelets, neutrophil counts, or other hematologic parameters.

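### The 2-in-9 DLT stop counts events only through Day 7, so later thrombocytopenia and events at up-titrated doses cannot trigger it

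*Combined protocol and SAP*

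**What the plan says.** Under Reporting Requirements, Section 11 states: "Stopping rules for this study include 2 DLT's in the first cohort of 9". It counts an event only if it "occurs through Day 7 of the Initial Treatment Period unless the event is considered by the Investigator to be clearly unrelated to IMG-7289". Section 6.5.2 and the synopsis use the same window. Two of the five listed DLTs concern platelets: "Any Grade 3 or above thrombocytopenia associated with clinically significant bleeding" and "Any Grade 4 thrombocytopenia associated with the requirement for platelet transfusion". The other three are non-hematologic or electrolyte events.

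Section 3.5 describes platelet kinetics from the myelofibrosis study CTP-102. It notes that at a given daily dose "the platelet count continues to fall beyond Day 7 of dosing", and gives mean changes at an identical dose of -31% from Day 7 to 14 (N=20) and about -12% from Day 14 to 21, "suggesting that a steady state of drug exposure, LSD1 activity and platelet production occurs between Day 21 and Day 28". The protocol uses these data to set a minimum of four weeks between up-titrations. Section 3.4 expects similar kinetics in ET and lists the safety of dose titration among the primary scientific goals. Sections 5.2, 6.1 and 6.2 put the first up-titration at ITP Day 29.

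**The concern.** The protocol judges one week too short to see the platelet effect of a dose when it sets the titration interval. It then uses one week as the whole observation window for its trial-level safety stop, and no text explains the choice. Two kinds of event fall outside the count: thrombocytopenia with bleeding or transfusion that develops after Day 7 at the starting dose, and any event at an up-titrated dose.

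What is at stake is the meaning of the result. A count of fewer than 2 DLTs in 9 patients describes the first week at 0.6 mg/kg. It says nothing about titrated dosing, which is what the trial sets out to study.

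**Working it through.** **The cohort of 9.** It is stage 1 of the Simon design in Section 10 (response rates 10% and 40%; stop if 1 or fewer of 9 respond, reject if 4 or fewer of 20). Exact enumeration reproduces this as the optimal design, with attained alpha 0.035, power 0.902 and early-stopping probability 0.775 at 10%. The protocol gives no operating characteristics for the DLT rule.

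**Platelet fall after the window closes (Section 3.5).** (1 - 0.31) × (1 - 0.12) = 0.69 × 0.88 = 0.607, a further mean fall of about 39% from Day 7 to Day 21. Multiplying two reported means is an approximation.

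**Timing of blood counts (Section 7.3.2).** The first scheduled on-treatment CBC belongs to the Day 8 visit, which may fall on Days 7 to 9, with blood drawn up to two days earlier. A patient on schedule may therefore have no CBC inside the window.

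**Titrated doses (Table 1).** If platelets stay above 400, the scheduled steps fall on Days 29, 57, 85, 113 and 141: 0.6 + 5 × 0.2 = 1.6 mg/kg/d by Day 141. None of these dose levels is reached inside the window. The only route to an earlier increase is the table's footnote allowing the PI to depart from it.

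**What the window could cost the rule.** With countable DLT rate q, P(2 or more of 9) = 1 - (1-q)^9 - 9q(1-q)^8. If the window catches a share c of events at true rate p, then q = c × p. The documents do not give c, so the values below are assumptions.

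| True rate p | c = 1 | c = 0.5 | c = 0.25 | c = 0.10 |
|---|---|---|---|---|
| 10% | 22.5% | 7.1% | 2.0% | 0.3% |
| 20% | 56.4% | 22.5% | 7.1% | 1.3% |
| 30% | 80.4% | 40.1% | 14.2% | 2.8% |

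**Can c be pinned down?** Take crossings below 50 × 10^9/L, the hold threshold in Table 1. Assume a lognormal Day 7 count with median B × (1 - f) and log-SD s, and the same 0.607 ratio to Day 21 for everyone. With m = ln[B(1 - f)], c = Φ[(ln 50 - m)/s] / Φ[(ln 50 - m - ln 0.607)/s]. For B = 450, f = 0.5, s = 0.6 this is 0.0061/0.0469 = 0.13. Across B of 450 or 700, f of 0.2 to 0.7 and s of 0.4 to 0.8, c runs from about 0 to 0.40. These are count crossings; a DLT also needs bleeding or transfusion. The range is too wide to support a single figure.

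**The case against.** A reader might infer that the rule is nearly blind to thrombocytopenia. The documents do not support that. They give neither the fall from Day 1 to Day 7 nor the timing of bleeding or transfusion. The measured changes come from myelofibrosis patients and end at Day 21; the later steady state is only suggested. Section 3.5 also does not say that the constant dose was the starting dose, so mapping its Day 7 onto ITP Day 7 is itself an inference.

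A second tempting figure is that a patient entering at 450 would have to fall 89% in a week to go below 50 (1 - 50/450). High entry counts drive this more than the window does. On mean kinetics, reaching 50 by Day 21 still needs a Day 7 count of about 82 (50/0.607), a first-week fall of about 82% (1 - 82.3/450). A 39% fall from 450 gives about 273, inside the 200 to 400 target. Absolute risk at the starting dose may well be low.

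There are also backstops: patient-level holds and discontinuation rules, continuous PI review that can suspend enrollment, DSMB approval before the next 11 patients, and an out-of-cycle report once three like events occur. The three DLT definitions agree with one another, and Section 3.5 was written to justify titration, so this is an unexplained choice and not a direct contradiction.

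All of that stands and limits the point. It does not remove it. None of the backstops sets a numerical halt. The synopsis and Section 6.5.1 say hematologic effects are not regarded as adverse, while the Section 11 adverse event definition includes abnormal laboratory findings. It is therefore unclear how late thrombocytopenia enters any event count. The exclusion of scheduled up-titrated doses follows from the dates alone and needs no kinetic assumption.

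**Conclusion.** The point holds in limited form. The trial-level stop cannot register thrombocytopenia DLTs that develop after Day 7 or events at doses reached by scheduled up-titration, and the protocol's own kinetics show a further mean platelet fall of about 39% after the window closes. This rests on the myelofibrosis data in Section 3.5 and on the protocol's expectation that ET behaves similarly. How much sensitivity is lost is unknown; the table shows how it depends on an assumed capture share.

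A reader might go further and infer that late toxicity goes unmonitored. It does not: early non-hematologic DLTs count toward the stop, and later events reach the PI and DSMB. The gap is in one numerical rule and in what its result can be said to show. It should be addressed, but it does not undermine the efficacy design.

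**What to change.** - Justify the Day 7 window in the synopsis, Section 6.5.2 and Section 11 against the kinetics in Section 3.5, or reconcile the passages. No window length is proposed here.
- At the nine-patient enrollment hold, give the DSMB the count of events meeting the DLT definitions on any day of the ITP, with study day and dose at onset, beside the Day 7 count.
- Record these events for that table even where the synopsis and Section 6.5.1 would treat the hematologic effect as not adverse.
- Do not present fewer than 2 DLTs in 9 as evidence on the safety of titrated doses.

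The data come from scheduled ITP visits (weekly to Day 57, bi-weekly to Day 113, then monthly), so later events are observed less closely than early ones. No visits are added, and the hold already waits for Week 24 response. The cost is protocol wording, one table and a count that may look less favorable.
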